163 We hypothesize that, as compared to the actual standard of care transition strategy (1:1 dose
164 conversion at the day of CSII to MDI transition), an alternative transition strategy will result in
165 lower time spent in hyperglycemia without increasing the risk for hypoglycemia. The alternative
166 strategy being (overlap transition strategy):

- 167 • Administration of insulin degludec at a 1:1 basal dose conversion dosage at day 0, with the
168 concomitant use of the insulin pump for 48 hours from transition, where CSII basal rate

169 will be reduced by 50% during the first 24 hours from transition and by 75% during 24 to
170 48 hours from transition. CSII will be disconnected after 48 hours from transition.

171 **3.2. Endpoints:**

172 Primary and secondary endpoints will be analyzed from 1-week of blinded CGM use during
173 randomization phase.

174 Primary endpoint:

175 1. Time spent in CGM glucose levels >180mg/dl

176 Secondary endpoints:

177 1. Time spent in CGM-measured “time-in-range”(glucose levels ≥ 70 mg /dl and ≤ 180 mg/dl)

178 2. Time spent in CGM-measured hypoglycemia < 70 mg/dl

179 3. Frequency of severe hypoglycemia as defined by the ADA (severe cognitive impairment
180 requiring external assistance for recovery) and severe hyperglycemia (BG \geq 250 needing
181 hospitalization)

182 4. Number of boluses (correction boluses) between groups during first 72 hours of
183 randomization

[figure not shown]
184 5. Patient-Reported Outcomes (PRO) using validated questionnaires; insulin delivery
185 satisfaction survey (IDSS) and Work Productivity and Activity Impairment Questionnaire:
186 Specific Health Problem V2.0 (WPAI: SHP) [18,19]

187 **3.3. Study design:**

188 • This is a 3-week, randomized control, open label, single center clinical trial with two study
189 arms comparing the efficacy and safety of the ‘standard of care transition’ and an ‘overlap
190 transition’ strategy

- 191 • The study consists of a screening phase, one week of run-in phase (blinded CGM
- 192 monitoring), one week of the experimental protocol following randomization phase and
- 193 one week of follow-up phase.
- 194 • Overall, the study will last 3 weeks that includes four clinical trial phases (**Figure 1**):
- 195 ○ Screening phase (Week 0): After informed consent, inclusion and exclusion, blinded CGM
- 196 will be inserted.
- 197 ○ Run-in phase (Week 0 to end of week 1): Subjects will wear blinded CGM and continue to
- 198 use CSII.

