270 anticipated change in physical activities or diet at the discretion of the investigators.
271
272

273 **5.3. Withdrawal criteria**

- 274 • Participation in this research is voluntary. Subjects may withdraw at will at any time. When
275 withdrawing from the study, the participant should let the research team know that he/she
276 wishes to withdraw. A participant may provide the research team with the reason(s) for
277 leaving the study, but is not required to provide their reason.
- 278 • Participants will be withdrawn from the study if they become pregnant, actively try to
279 become pregnant, develop an allergic reaction to insulin/adhesives, severe episodes of
280 hypoglycemia/hyperglycemia, or at the judgement of investigators due to safety concerns,
281 such as abnormality in laboratory exam results.
- 282 • After withdrawal, the participant will be given instructions on how to safely stop using
283 study medications and, eventually, on how to correctly and safely return to the previous
284 insulin regimen. Instructions are also given on who to contact if there are any questions or
285 concerns that arise after study withdrawal.
- 286 • At the time of withdrawal, the research participant should let the research team know if
287 he/she will allow the use of his/her health information and collected data by the researchers.

288 **5.4. Subject replacement**

289 Subject replacement will occur only if withdrawal occurs before the one-week randomization
290 phase. Subjects will not be replaced during the one-week randomized phase.

291 **5.5. Rationale for study population**

292 In anticipation of screening failure or withdrawal or anticipated issues due to covid-19 pandemic,
293 we plan to screen up to 40 subjects to have 30 complete the clinical trial.

294

295

296 **6. VISIT PROCEDURES:**

297 **6.1. Visit 1, week 0, day0, screening and blinded CGM insertion**

- 298 ▪ Subjects will attend a screening visit (Visit 1, week 0) in order to assess eligibility for the
299 study.
- 300 ▪ Before screening takes place, subjects will be provided with written information about the
301 trial and the procedures involved. Subjects will be fully informed, both orally and in
302 writing, about their responsibilities and rights while participating in the trial, as well as
303 about possible advantages and disadvantages when participating in this trial. Subjects will
304 have the opportunity to ask questions and have ample time to consider participation. The

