491 **6.8. Assessments for Safety:**

492 The following safety assessments will be performed;

- 493 ▪ Time spent in CGM measured hypoglycemia (< 70 mg/dl) and time spent in hyperglycemia
- 494 (≥250 mg/dl)
- 495 ▪ AE/SAE
- 496 ▪ Documented hypoglycemic episodes
- 497 ▪ Height, weight, vitals and physical examination
- 498 ▪ Baseline laboratory assessment
- 499 ▪ Hypoglycemia unawareness assessment (using GOLD questionnaire)
- 500 ▪ Pregnancy test at screening

501 **6.9. Assessments for Efficacy:**

502 The assessment for efficacy is time spent in CGM glucose time-in-range (min/ 24 hours, 70-180
503 mg/dl) during the 7 days of randomization period.

504 **7. EVALUABILITY OF SUBJECTS:**

505 The data for a subject with minimum of 5 out of 7 days of blinded CGM prior to randomization
506 and 5 out of 7 days of blinded CGM after randomization will be evaluable and included for the
507 analysis of primary and secondary objectives.

508 **8. STATISTICAL CONSIDERATIONS:**

509 **8.1. Sample size calculation**

510 In a study by Garg and colleagues, the subjects with T1D on MDI and blinded CGM for first 4
511 weeks of the study spent average of 8.8 hours/day (~528 min/ 24 hours) in CGM defined glucose
512 above 180 mg/dl [21]. Similarly, in the recently published DIAMOND study, subjects on MDI
513 using CGM experienced average of 601 minutes (~10 hours/ day, IQR; 467-793 min) per 24 hours

514 of time spent in hyperglycemia [22]. We assume that subjects in standard of care group would
515 have more hyperglycemia than subjects in overlap transition group. Therefore, the expected CGM
516 hyperglycemia is ~ 650 minutes/24 hours in standard of care and ~ 500 minutes/24 hours in
517 overlap transition group with the differences in CGM glucose by 150 minutes/day between the
518 groups.

519 This study is powered based on the primary endpoint, which is time spent in CGM-measured
520 glucose levels >180mg/dl (hyperglycemia). We have based the sample size on minimal relevant
521 differences between the two treatment groups, using a Type I error rate of 5% and a Type II error
522 rate of 20%. We hypothesize that the primary endpoint, time in minutes spent with glucose levels
523 >180 mg/dl, will be higher in the standard treatment group than in the experimental group (overlap
524 transition group), but we will use a two-sided test to assess differences in hyperglycemia by
525 treatment group. We hypothesize a standard deviation (SD) for time spent in hyperglycemia of

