552 univariate differences between the standard care group and the experimental group for each of the
553 outcomes. Secondary endpoints include time in range (70-180 mg/dl), time spent hypoglycemic
554 (<70 mg/dl), frequency of severe hypoglycemia, number of correction boluses, and patient
555 reported outcomes as defined on the page 7 of the protocol. Secondary endpoints will be
556 examined using student's t-test to compare these outcomes univariately between the standard care
557 and experimental groups. In a sensitivity analysis, CGM metrics will be evaluated in the first 72
558 hours vs entire 1 week as we expect that differences in hyperglycemia and time-in-range will be
559 more pronounced between the two groups in the first 72 hours. For both primary and secondary
560 endpoints, linear regression analysis will be used to examine outcomes by treatment group while
561 adjusting for potential residual confounders, such as age and sex, which may not be fully
562 addressed by randomization. All testing will be two-sided. The analysis will be conducted as an
563 intention-to-treat analysis.

564 **9. DATA HANDLING AND RECORD KEEPING:**

- 565 ▪ All data generated during the study will be retained by the investigator. Safety events will
566 be reported to Colorado Multiple Institutional Review Board (COMIRB) in a timely
567 manner as described under "Adverse Events".
- 568 ▪ Data management is the responsibility of the investigator. All paper and electronic data
569 will be saved in a de-identifiable manner. The data will be stored on BDC computers
570 which are secured by the University of Colorado servers. The data will be accessible only

571 by the study team and if transfer of data needed, appropriate measures, including
572 encryption of data files will be used to ensure security and subject confidentiality.

- 573 ■ The records will be stored securely and kept for minimum of 10 years per the Standards
574 Operating Procedures (SOP) of the University of Colorado [23].
575 [[http://www.ucdenver.edu/research/Research%20Administration%20Documents/COMIRB
-Policy-and-Procedures-Document.pdf](http://www.ucdenver.edu/research/Research%20Administration%20Documents/COMIRB
576 -Policy-and-Procedures-Document.pdf)]

577 **10. ETHICS:**

- 578 ■ The trial will be conducted in compliance with this protocol, ICH GCP, the University of
579 Colorado COMIRB research policy and in accordance with the Declaration of Helsinki
580 [23-25].

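### The 5-of-7-day CGM rule covers every endpoint, so an early severe event can drop a participant from the endpoint that counts it

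*Combined protocol and SAP*

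**What the plan says.** Four provisions of the combined protocol and SAP have to be read together.

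- **Withdrawal (5.3).** "Participants will be withdrawn from the study if they become pregnant, actively try to" continues as "become pregnant, develop an allergic reaction to insulin/adhesives, severe episodes of" hypoglycemia or hyperglycemia. The section then covers stopping study drug safely, returning to the previous regimen, and asking whether "he/she will allow the use of his/her health information and collected data by the researchers". It does not mention leaving the blinded sensor in place.
- **Evaluability (7).** A participant with at least 5 of 7 CGM days before randomisation "and 5 out of 7 days of blinded CGM after randomization will be evaluable and included for the" "analysis of primary and secondary objectives". No endpoint is exempted.
- **Endpoints (3.2).** Secondary endpoint 3 begins "Frequency of severe hypoglycemia as defined by the ADA (severe cognitive impairment" and also covers severe hyperglycemia leading to hospitalisation. Secondary endpoint 4 begins "Number of boluses (correction boluses) between groups during first 72 hours of" randomisation; section 6.3 has these recorded in a diary. Neither needs a CGM trace.
- **Analysis principle (8.2).** "All testing will be two-sided. The analysis will be conducted as an" intention-to-treat analysis. Nothing reconciles this with section 7, and no method for missing data is given.

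Section 6.4 adds that severe events found at the 24- and 48-hour calls are recorded as SAEs and that the insulin dose may be modified at the investigator's discretion.

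**The concern.** For endpoint 3, membership of the analysis set can depend on the outcome itself. A participant who has an early severe event and leaves cannot reach 5 CGM days, so the rule that defines who is counted removes the person who should be counted. For endpoint 4, a complete observation can be discarded because of sensor days that the endpoint does not use.

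The hypothesis in section 3.1 is less hyperglycemia with no added risk of hypoglycemia. In the overlap arm (6.3), full-dose degludec is combined with half, then a quarter, of the pump basal rate over the first 48 hours. Severe hypoglycemia caused by the overlap would plausibly fall inside the exposed window, and its loss would favour the new strategy on endpoint 3 and on time below 70 mg/dl. Losing a severe hyperglycemia case from standard care would work the other way and understate the primary difference, which is conservative.

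**Working it through.** **1. The plan's own figure.** Section 8.1 gives 15 completers per arm, SD 140 min, two-sided 5%, 80% power and a detectable difference of 148.4 min. For a two-sample t-test with 28 df and noncentrality d/√(1/15 + 1/15), 80% power needs d = 1.0598, and 1.0598 × 140 = 148.4 min. This matches. At d = 1.06, 14 against 15 gives 78.5% power, compared with 80.0% for 15 against 15. Loss of numbers is not the problem.

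**2. Following one participant through the rules.** Assume the run-in CGM is adequate, the severe event leads to exit under 5.3, and the sensor stops at exit. The last is the natural reading of 5.3, not an explicit statement.

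| Time of exit after randomisation | CGM days | CGM endpoints | Endpoint 3 | Endpoint 4 |
|---|---|---|---|---|
| Before 72 h | under 3 | out | out, though the event is known | out; diary incomplete anyway |
| 72 to 120 h | 3 to under 5 | out | out, though the event is known | out, though the diary is complete |
| After 120 h | 5 or more | in | in | in |

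The middle row covers 48/120 = 40% of the exposed time. That is a share of time, not of events; section 6.1 expects hyperglycemia mainly in the first 48 to 72 hours.

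**3. Effect of one event on endpoint 3 (Clopper-Pearson 95% limits).**
- All randomised in that arm: 1/15 = 6.7% (0.2% to 31.9%).
- After section 7: 0/14 = 0% (0% to 23.2%).

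**4. How likely is this?** The documents give no event rate, so the rates r below are assumptions. Exposure is 30 × 5/365.25 = 0.411 person-years, and P(at least one event) = 1 − exp(−0.411 r).
- r = 0.1 per person-year: 4.0%
- r = 0.5: 18.6%
- r = 1.0: 33.7%

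Section 5.2 excludes recent severe hypoglycemia, recent hospitalised DKA and a GOLD score of 4 or more, which argues for the lower rates.

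**5. CGM endpoints, for scale.** If the excluded participant's weekly mean lay k SDs from the mean of the other 14, the arm mean would shift by k × SD/15. The values k = 1 to 3 are assumed.
- Time above 180 mg/dl, SD 140: 140/15 = 9.3 to 3 × 140/15 = 28.0 min/day, which is 6.3% to 18.9% of 148.4.
- Time below 70 mg/dl, SD 45 to 75: 45/15 = 3.0 to 3 × 75/15 = 15.0 min/day, the same 6.3% to 18.9% of the detectable differences of 47.7 to 79.5.

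These treat the deviation as lasting all week. If the participant returned to the pump and it ended sooner, the shift would be smaller.

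**The case against.** **Exit is not settled.** Section 6.4 provides for dose modification after a severe event, which makes little sense for someone who must leave, and section 6.1 likewise treats severe episodes in the run-in as managed. This stands: exit is likely but not certain. It does not cancel 5.3, and the two sections should be aligned.

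**Section 7 is really a rule about enough CGM data.** On that view an analyst could count endpoint 3 in everyone randomised and rely on the intention-to-treat statement. That may well be the intent. The text, however, applies the rule to primary and secondary objectives without distinction, so loss from endpoints 3 and 4 is its literal consequence.

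**The practical effect is close to nil.** This largely stands. With no events in the other arm, Fisher's exact test gives p = 1.0 for 1/15 against 0/15, and 0/14 against 0/15 shows no difference either. The event rates and SD shifts above are assumed. Severe events are also only one route into the gap: section 14 anticipates sensors that last fewer than 7 days.

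**A reader might infer that the plan hides severe events.** The documents do not support that. Section 6.4 records them as SAEs, section 6.8 lists AE/SAE and documented hypoglycemic episodes, and section 14 collects adverse events to the end of follow-up. The loss is from the randomised comparison, not from safety reporting.

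**Conclusion.** The point holds as a minor defect in how the analysis sets are defined. Section 7 applied literally allows an outcome-dependent exclusion from endpoint 3 and an unnecessary one from endpoint 4, and it contradicts the intention-to-treat label in 8.2. The illustration is 1/15 becoming 0/14 in one arm. This rests on exit following the event, on the sensor stopping at exit, and on section 7 meaning what it says for endpoints that do not use CGM.

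Two stronger inferences are not supported. One is that the trial loses material power: a single loss costs 1.5 percentage points. The other is that the primary result would be materially biased: that depends on event rates and deviations the documents do not give, and the hyperglycemia they do anticipate, in standard care, would bias conservatively. The case for the change is that the rule is wrong in principle and easy to correct, not that a large distortion is expected.

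**What to change.** In sections 7 and 8.2:

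- Limit the 5-of-7-day rule to the CGM endpoints.
- Count endpoint 3 in all randomised participants, by assigned arm, regardless of CGM days.
- Analyse endpoint 4 in every randomised participant with a 72-hour diary.
- Describe the 5-of-7-day CGM analysis as an evaluable-set analysis, not intention-to-treat. Add a sensitivity analysis that includes participants with shorter records and accounts for which days were observed, for example a model of daily minutes with arm, day and their interaction. Simple averages should not be pooled: hyperglycemia is expected mainly in the first 72 hours, so a one- or two-day record would over-weight the worst period.

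Optionally, state in 5.3 that a severe episode after randomisation ends the assigned treatment, while the blinded sensor already in place and adverse-event contact continue if the participant agrees; align 6.4 with this. Personal real-time CGM should not be opened up as part of the change, since section 3.4 says it would interfere with the outcomes.

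The cost is a short wording amendment using data already collected, slightly different denominators across endpoints, and one extra sensitivity analysis. The safety stop is unchanged.

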423 one unit of rapid acting insulin will drop blood glucose. For example; a patient with
424 carbohydrate ratio of 1:15 and correction factor of 1:50 >150 will take 3 units if preprandial
425 blood glucose is ~200 mg/dl for 30 grams of meal (2 units for 30 grams of carbs + 1 unit for
426 correction). Subjects randomized to group 2 will be instructed to start insulin aspart 48 hours
427 after randomization; i.e. when they disconnect their insulin pump.
- 428 ▪ It is likely that patients randomized to standard-of-care group may experience
429 hyperglycemia during first 48-72 hours. Therefore, both groups will be given a diary
430 (**Appendix 1**) to record any correction made during the randomization phase to count extra
431 insulin injections needed to correct blood glucose during first 72 hours.

432 **6.4. Phone call 1 [P1, week 2, visit 2+24hrs] and phone call 2 [P2, week 2, P1+24hrs]**

- 433 ▪ As a safety measures, there will be 2 phone calls 24 and 48 hours after randomization,
434 respectively.
- 435 ▪ Phone call 1 (P1) will be done 24 hours (± 6 hours in case if patient does not respond to first
436 phone call) after visit 2.
- 437 ▪ Phone call 2 (P2) will be done 24 hours (± 6 hours in case if patient does not respond to first
438 phone call) after P1.
- 439 ▪ All subjects will be asked/assessed for

- 440 ○ Any episodes of severe hyperglycemia requiring hospitalization or hypoglycemia
- 441 requiring third person' assistance. These events will be recorded as SAE and insulin
- 442 dose modification will be done at discretion of the investigator for safety reasons.
- 443 ○ Correct insulin dose and administration will be reassessed.
- 444 ○ Maintenance of glucose and insulin injection dairy.
- 445 ○ Any skin reaction at CGM site.
- 446 ■ For Group 2 (overlap transition):
- 447 ○ Instructions to change in basal rate (75% basal reduction) will be done at P1
- 448 ○ Instructions for CSII discontinuation and initiation of insulin aspart based on
- 449 carbohydrate ratio and correction factor at P2

450 **6.5. Visit 3, week 2, day 14±1: end of treatment**

- 451 ■ Blood glucose meter download and review of SMBG.
- 452 ■ Subject's blinded CGM will be removed and downloaded.
- 453 ■ Look for any local skin reaction at the site of CGM insertion.
- 454 ■ Subjects will return all the remained study-related products (CGM device components,
- 455 insulin degludec and aspart pens, and any auxiliary supplies)
- 456 ■ Report any AE/SAE if any.

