721 Suspected Unexpected Serious Adverse Reactions (SUSAR)

722 An unexpected adverse reaction (UAR) is an adverse reaction that is not consistent with the

723 product information in the summary of product characteristics (SPC, i.e.US prescribing

724 information). The current version or any updated if available during the clinical trial for US
725 prescribing information for study drugs will be used as SPC. If UAR is severe enough to define as
726 SAE is called as SUSAR.

727 Technical complaint

728 A technical complaint is any written, electronic, or oral communication that alleges product
729 (medicine or device) defects. The technical complaint may be associated with an AE, but does not
730 concern the AE itself.

731 Reportable Device Issues

732 AE and Unexpected Adverse Device Events (UADE) arising from the use of blinded CGM
733 (Dexcom G6) will be reported irrespective of severity, except in following circumstances:

734 The following device issues are anticipated and will not be reported unless the criteria for AE
735 reporting described above are met

- 736 • Component disconnections
- 737 • CGM sensors lasting fewer than 7 days
- 738 • CGM tape adherence issues
- 739 • Battery lifespan deficiency due to inadequate charging or extensive wireless
740 communication
- 741 • Intermittent device component disconnections/communication failures not leading to
742 system replacement
- 743 • Device issues clearly addressed in the user guide manual that do not require additional
744 troubleshooting
- 745 • Skin reactions from CGM sensor placement that don't meet criteria for AE reporting

746

747 **Safety Monitoring Officer**

748 A safety-monitoring officer ([name]) will independently monitor the study, including
749 adverse events and study drug or device issues with potential to impact participant safety. A
750 monthly meeting will be held between study team and the safety officer to review any adverse
751 events. Following each safety review, a summary recommendation from the safety monitoring
752 officer will be collected.

753 Reporting and follow-up of adverse events

754

755 All events meeting the definition of an AE must be collected and reported. This includes events
756 from the first trial-related activity after the subject has signed the informed consent until the end of
757 the post-treatment follow-up period.

758 During each contact, the trained professional research associate will ask the subject about AEs and

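### Participants withdrawn for severe glycemic episodes may refuse use of data already collected, and the CGM-day rule drops early withdrawals anyway, so randomized participants with events can be selectively lost despite the intention-to-treat statement

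*Combined protocol and SAP*

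**What the plan says.** Five parts of the combined protocol and SAP bear on this point.

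- **Section 5.3 (Withdrawal criteria).** Participants are to be withdrawn if they "become pregnant, develop an allergic reaction to insulin/adhesives, severe episodes of" hypo- or hyperglycemia, among other reasons. At withdrawal the participant should tell the team whether "he/she will allow the use of his/her health information and collected data by the researchers". This covers data already obtained. The section does not say what is retained if the answer is no. Section 5.4 adds: "Subjects will not be replaced during the one-week randomized phase".
- **Section 3.2 (Endpoints).** Secondary endpoint 3 is "Frequency of severe hypoglycemia as defined by the ADA (severe cognitive impairment" with need for outside help), together with severe hyperglycemia leading to hospital admission.
- **Section 6.4 (Phone calls 1 and 2).** For hyperglycemia needing hospital care, or hypoglycemia "requiring third person' assistance. These events will be recorded as SAE and insulin" "dose modification will be done at discretion of the investigator for safety reasons". Withdrawal is not mentioned there.
- **Sections 7 and 8.2.** A participant is evaluable for primary and secondary objectives only with at least 5 of 7 blinded CGM days both before and after randomization. Section 8.2 says "The analysis will be conducted as an" intention-to-treat analysis and gives no missing-data method.
- **Section 14.** "All events meeting the definition of an AE must be collected and reported", from consent to the end of follow-up, with no exception for people who withdraw.

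**The concern.** The question about data use is put after the outcome has occurred, to a group defined partly by that outcome, and by people who know their arm. The protocol puts no such question to completers. If a participant with a severe episode is withdrawn and refuses, an endpoint 3 event and that participant's CGM record can leave the randomized comparison.

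The hypothesis in Section 3.1 is less hyperglycemia without more hypoglycemia risk. With 15 per arm and a one-week randomized phase, severe events will be few, so the safety half of that claim could turn on one or two participants. Nothing in the plan limits the loss: there is no replacement after randomization, no missing-data method, and no report of refusals by arm.

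**Working it through.** **1. The plan's own figure.** Section 8.1 gives SD 140 min, two-sided 5%, 15 completers per group, and 80% power for 148.4 min. The effect size is d = 148.4/140 = 1.06. For a two-sample t-test, power comes from the noncentral t distribution with n1 + n2 − 2 degrees of freedom and noncentrality d × √(n1·n2/(n1 + n2)). With 15 v 15 the noncentrality is 1.06 × √7.5 = 2.90 and power is 80.0%. The stated figure reproduces.

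**2. Loss unrelated to outcome, in one arm.**

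| Completers | Noncentrality | Power |
|---|---|---|
| 15 v 15 | 2.90 | 80.0% |
| 15 v 14 | 1.06 × √(210/29) = 2.85 | 78.5% |
| 15 v 13 | 1.06 × √(195/28) = 2.80 | 76.8% |
| 15 v 12 | 1.06 × √(180/27) = 2.74 | 74.9% |

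Losing one in each arm (14 v 14) gives 77.0%, and two in each arm (13 v 13) gives 73.7%.

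**3. Loss related to outcome, worst case.** Assume normal data with the plan's expected means of 650 and 500 min and SD 140, and remove the highest standard-care values (100,000 simulated trials).

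| Highest standard-care values lost | Expected difference | Power |
|---|---|---|
| 0 | 150 min | about 81% |
| 1 | about 133 min | 72% |
| 2 | about 118 min | 63% |
| 3 | about 104 min | 52% |

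This is an extreme case, because a severe episode need not coincide with the highest weekly time above 180 mg/dl. Here the loss shrinks the overlap arm's apparent benefit.

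**4. Endpoint 3.** Removing one participant with an event takes an arm from 1/15 (6.7%) to 0/14 (0%). The documents give no event or refusal rate, so both are assumed. If a proportion p of the 30 have an event and are withdrawn, and a proportion r of those refuse, the chance of losing at least one is 1 − (1 − p·r)^30.

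| p | Expected events (30p) | r = 10% | r = 25% | r = 50% |
|---|---|---|---|---|
| 2% | 0.6 | 6% | 14% | 26% |
| 5% | 1.5 | 14% | 31% | 53% |
| 10% | 3.0 | 26% | 53% | 79% |

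**5. The Section 7 route.** The protocol expects the difficult period to be the first 48 to 72 hours. Someone withdrawn then has about 2 to 3 CGM days after randomization if wear stops at withdrawal, which is fewer than 5. On the literal text that person drops out of primary and secondary analyses whether or not data use is allowed. Endpoint 3 is among the secondary endpoints, although it does not depend on CGM. Changing Section 5.3 alone would therefore not bring early withdrawals back.

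**6. Sections 5.3 and 6.4 side by side.** One says that participants with severe episodes will be withdrawn. The other describes SAE recording and discretionary dose modification. How often the data-use question follows a severe event depends on which is applied, and the documents do not settle that.

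**The case against.** The strongest reply is that several things must happen before anything is lost: a severe event, then withdrawal, then a refusal. The question goes to everyone who withdraws, including for pregnancy, allergy, laboratory findings or personal choice. A reader might infer that the clause removes precisely the participants with events. The text does not support that; it makes selective loss possible, not automatic.

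A reader might also infer that the duty to report every adverse event cannot be met. That goes too far. The event precedes withdrawal, Section 6.4 has it recorded as an SAE, and Section 14 sets recording and reporting times with no exception for withdrawal. The safety record probably survives. What stays open is whether a refusal bars the event from the endpoint 3 comparison, because Section 5.3 covers health information and collected data without exempting adverse events.

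Third, a bias toward showing no harm is not established for CGM time. The protocol expects the excess hyperglycemia under standard care, and losing high values there works against the trial's hypothesis. CGM is blinded, so participants do not know their CGM totals when they choose, though they do know their arm and their event.

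Finally, eligibility excludes recent severe hypoglycemia, recent ketoacidosis requiring hospitalization and impaired awareness, so events may be rare. One event against none cannot support a formal comparison in any case (Fisher's exact p = 1.0 at 15 v 15). That is fair, but it does not make the count less important as a description of safety.

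**Conclusion.** The concern stands as a gap that permits selective loss of randomized participants, not as a demonstrated bias. It rests on three features of the text: the data-use choice reaches back to collected data, severe glycemic episodes are a listed withdrawal reason, and endpoint 3 counts that type of event in an open-label trial. Section 7 reaches a similar result by a separate and more certain route, and it too conflicts with the intention-to-treat statement.

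The power cost is small: 80.0% to 78.5% for one lost participant. Power near 77% or 74% is reached only by losing one or two from both arms, that is, two or four people. The larger exposure is endpoint 3, where one lost participant could be an arm's only event. How likely that is cannot be taken from the documents; the 6% to 79% range reflects assumed event and refusal rates only.

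**What to change.** 1. **Section 5.3, for newly consented participants:** state that data and adverse events collected up to withdrawal are retained and analysed in the randomized arm, and ask only whether further data may be collected. Make the same change in the consent form if it has matching wording; the consent pages were not available for this review. Anyone already consented keeps the choice they were promised.
2. **Endpoint 3:** count events in all randomized participants, regardless of CGM days.
3. **Sections 7 and 8.2:** reconcile the 5-of-7-day rule with intention-to-treat, and add a sensitivity analysis for missing CGM data.
4. **Reporting:** give withdrawals, their reasons where offered, and any data-use refusals by arm.
5. **Sections 5.3 and 6.4:** reconcile what follows a severe event.

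The cost is a few sentences of protocol text, IRB review, and two consent wordings within a small trial, since the table of protocol changes shows that enrollment had already begun. If the IRB requires the opt-out to stay, the minimum is to state that adverse events and endpoint 3 events are kept, and to report refusals by arm.
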